7.6. Treatment Compliance

Patient compliance with study medication will be assessed at the dosing visit. Deviation(s) from the prescribed dosage regimen should be recorded in the electronic case report form (eCRF).

7.7. Concomitant Therapy

The list of excluded medications and procedures is provided in the Manual of Operations. Any changes in the list of allowed/not allowed medications will be communicated to investigators and will not constitute a protocol amendment.

7.8. Treatment after the End of the Study

Study treatment will not be made available to patients after conclusion of the study.

8. Discontinuation Criteria

8.1. Discontinuation from Study Treatment

8.1.1. *Permanent Discontinuation from Study Treatment*

Possible reasons leading to permanent discontinuation of study treatment:

- **Subject Decision**
 - the patient requests to discontinue study treatment.
- In addition, patients will be discontinued from the study treatment in the following circumstances:
 - WMC retention or aspiration

Patients discontinuing from the study prematurely for any reason should complete AE and other follow-up procedures per Section 2 (Schedule of Activities), Section 9.2 (Adverse Events), and Section 9.4 (Safety) of this protocol.

8.1.2. *Temporary Discontinuation from Study Treatment*

Not applicable.

8.1.3. *Discontinuation of Inadvertently Enrolled Patients*

If the sponsor or investigator identifies a patient who did not meet enrollment criteria and was inadvertently enrolled, then the patient should be discontinued from study treatment unless there are extenuating circumstances that make it medically necessary for the patient to continue study treatment. If the investigator and the sponsor clinical research physician (CRP)/clinical research scientist (CRS) agree it is medically appropriate to continue, the investigator must obtain documented approval from the sponsor CRP/CRS to allow the inadvertently enrolled patient to continue in the study with or without study treatment. Safety follow-up is as outlined in Section 2 (Schedule of Activities), Section 9.2 (Adverse Events), and Section 9.4 (Safety) of the protocol.

8.2. Discontinuation from the Study

Patients will be discontinued in the following circumstances:

- enrollment in any other clinical study involving an study treatment or enrollment in any other type of medical research judged not to be scientifically or medically compatible with this study
- participation in the study needs to be stopped for medical, safety, regulatory, or other reasons consistent with applicable laws, regulations, and Good Clinical Practice (GCP)
- investigator decision

- the investigator decides that the patient should be discontinued from the study
- if the patient, for any reason, requires treatment with another therapeutic agent that has been demonstrated to be effective for treatment of the study indication, discontinuation from the study occurs prior to introduction of the new agent
- patient decision
 - the patient requests to be withdrawn from the study
- patient becomes pregnant.

Patients discontinuing from the study prematurely for any reason should complete AE and other safety follow-up per Section 2 (Schedule of Activities), Section 9.2 (Adverse Events), and Section 9.4 (Safety) of this protocol.

8.3. Lost to Follow-Up

A patient will be considered lost to follow-up if he or she repeatedly fails to return for scheduled visits and is unable to be contacted by the study site. Site personnel are expected to make diligent attempts to contact patients who fail to return for a scheduled visit or were otherwise unable to be followed up by the site.

Site personnel, or an independent third party, will attempt to collect the vital status of the patient within legal and ethical boundaries for all patients randomized, including those who did not receive study treatment. Public sources may be searched for vital status information. If vital status is determined, this will be documented and the patient will not be considered lost to follow-up.

Lilly personnel will not be involved in any attempts to collect vital status information.

9. Study Assessments and Procedures

Section 2 lists the Schedule of Activities, with the study procedures and their timing (including tolerance limits for timing).

9.1. Efficacy Assessments

9.1.1. Primary Assessment of GI Transit Time

The WMC (Medtronic 2017) measures whole gut and regional gut (stomach, small bowel, and colon) transit times through measurement of pH, pressure, and temperature throughout the GI tract. Once enrolled into study, the patient will be asked to eat a SmartBar, followed by ingesting the WMC with 120 mL of water. The patient will then be instructed to fast for an additional 6 hours after the WMC is administered and wear an external data recorder for up to 5 days. The WMC is a 4.5-g indigestible single-use, 27 × 12 mm cylindrical capsule. Data are transferred to the accompanied wearable external data recorder and displayed and analyzed using MotiliGI™ version 3.1 software (Medtronic 2017).

The baseline and postbaseline WMC test will be assessed by expert readers who are blind to treatment assignment.

9.1.2. Secondary Assessment Scales

Gastrointestinal Symptom Rating Scale. The Gastrointestinal Symptom Rating Scale (GSRS) is a validated 15-item questionnaire that evaluates the 5 common symptoms of GI disorders: abdominal pain, reflux, indigestion, constipation, and diarrhea. Items ask about the past week using a 7-point categorical response scale from no discomfort to very severe discomfort (Revicki et.al 1998; Khanna 2017).

Bristol Stool Form Scale. The Bristol Stool Form Scale (BSFS) is a 7-point ordinal scale of stool types ranging from the hardest (Type 1) to the softest (Type 7). Symptoms of constipation are related to harder stools (Types 1 and 2) and symptoms of diarrhea are related to loose/liquid stools (Types 6 and 7). Overall, stool Type 3 to 5 are considered normal. BSFS provides the patient with a pictorial representation of each type of stool (Blake et al. 2016).

9.1.3. Appropriateness of Assessments

The efficacy and safety assessments used in this study have been well documented and are generally regarded as reliable, accurate, and are relevant for use in this study.

9.2. Adverse Events

Investigators are responsible for monitoring the safety of patients who have entered this study and for alerting Lilly or its designee to any event that seems unusual, even if this event may be considered an unanticipated benefit to the patient.

The investigator is responsible for the appropriate medical care of patients during the study.

Investigators must document their review of each laboratory safety report.

The investigator remains responsible for following, through an appropriate health care option, AEs that are serious or otherwise medically important, considered related to the study treatment or the study, or that caused the patient to discontinue the study treatment before completing the study. The patient should be followed up until the event resolves, stabilizes with appropriate diagnostic evaluation, or is reasonably explained. The frequency of follow-up evaluations of the AE is left to the discretion of the investigator.

Lack of drug effect is not an AE in clinical studies, because the purpose of the clinical study is to establish treatment effect.

The investigator will record all relevant AE and SAE information in the eCRF. After the ICF is signed, study site personnel will record via eCRF the occurrence and nature of each patient's preexisting conditions, including clinically significant signs and symptoms of the disease under treatment in the study. In addition, site personnel will record any change in the condition(s) and any new conditions as AEs. Investigators should record their assessment of the potential relatedness of each AE to protocol procedure and study treatment, via eCRF.

The investigator will interpret and document whether or not an AE has a reasonable possibility of being related to study treatment, study device, or a study procedure, taking into account the disease, concomitant treatment, or pathologies.

A "reasonable possibility" means that there is a cause-and-effect relationship between the study treatment, study device, and/or study procedure and the AE.

The investigator answers yes/no when making this assessment.

Planned surgeries and nonsurgical interventions should not be reported as AEs unless the underlying medical condition has worsened during the course of the study.

If a patient's study treatment is discontinued as a result of an AE, study site personnel must report this to Lilly or its designee via eCRF, clarifying if possible the circumstances leading to any dosage modifications, or discontinuations of treatment.

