9.2.1. Serious Adverse Events

An SAE is any AE from this study that results in 1 of the following outcomes:

- death
- initial or prolonged inpatient hospitalization
- a life-threatening experience (i.e., immediate risk of dying)
- persistent or significant disability/incapacity
- congenital anomaly/birth defect

- important medical events that may not be immediately life-threatening or result in death or hospitalization but may jeopardize the patient or may require intervention to prevent one of the other outcomes listed in the definition. Examples of such medical events include allergic bronchospasm requiring intensive treatment in an emergency room or at home, blood dyscrasias or convulsions that do not result in inpatient hospitalization, or the development of drug dependency or drug abuse.
- when a condition related to the AI pen necessitates medical or surgical intervention to preclude either permanent impairment of a body function or permanent damage to a body structure, the serious outcome of “required intervention” will be assigned.

All AEs occurring after signing the ICF are recorded in the eCRF and assessed for serious criteria. The SAE reporting to the sponsor begins after the patient has signed the ICF and has received study treatment. However, if an SAE occurs after signing the ICF, but prior to receiving study treatment, the SAE should be reported to the sponsor as per SAE reporting requirements and timelines (see Section 9.2) if it is considered reasonably possibly related to study procedure.

Study site personnel must alert Lilly or its designee of any SAE within 24 hours of investigator awareness of the event via a sponsor-approved method. If alerts are issued via telephone, they are to be immediately followed by official notification on study-specific SAE forms. This 24-hour notification requirement refers to the initial SAE information and all follow-up SAE information.

Pregnancy (during maternal or paternal exposure to study treatment) does not meet the definition of an AE. However, to fulfill regulatory requirements any pregnancy should be reported following the SAE process to collect data on the outcome for both mother and fetus.

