Investigators are not obligated to actively seek AEs or SAEs in subjects once they have discontinued and/or completed the study (the patient disposition eCRF has been completed). However, if the investigator learns of any SAE, including a death, at any time after a subject has been discharged from the study, and he or she considers the event reasonably possibly related to the study treatment or study participation, the investigator must promptly notify Lilly.

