9.2.1.1. Suspected Unexpected Serious Adverse Reactions

Suspected unexpected serious adverse reactions (SUSARs) are serious events that are not listed in the galcanezumab IB or the erenumab US package insert (USPI) and that the investigator identifies as related to study treatment or procedure. United States 21 CFR 312.32 and European Union Clinical Trial Directive 2001/20/EC and the associated detailed guidances or national regulatory requirements in participating countries require the reporting of SUSARs. Lilly has procedures that will be followed for the identification, recording, and expedited reporting of SUSARs that are consistent with global regulations and the associated detailed guidances.

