## 6.11. Safety Analyses

Unless specified otherwise, safety analyses outlined in the following subsections will be conducted for the safety population.

The safety and tolerability of treatment will be assessed by summarizing

- TEAEs
  - by PT
  - by PT nested within SOC
  - by maximum severity
  - by investigator classification of related to study treatment
- serious adverse events (SAEs) by PT
- AEs leading to discontinuation by PT, and
- vital signs.

Baseline for all safety measures includes all data prior to injection of study treatment. Postbaseline includes all data in Study Period II from injection of study treatment to completion of Study Period II.

For safety categorical variables and categorical variables of demographics and baseline characteristics, comparisons between treatment groups will be performed using Fisher's exact test. For continuous variables of demographics and baseline characteristics, an analysis of variance (ANOVA) with treatment as an independent variable in the model will be performed.

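### Protocol 9.2 asks whether an AE has a reasonable possibility of being related, but defines that term as causation existing, so possibly related events can be classified as unrelated

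*Protocol*

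**What the plan says.** Protocol Section 9.2 has the investigator interpret and document "whether or not an AE has a reasonable possibility of being related to study treatment, study device, or a study procedure". The next sentence defines reasonable possibility: it "means that there is a cause-and-effect relationship between the study treatment, study device, and/or study procedure and the AE". The response is binary: "The investigator answers yes/no when making this assessment". Shortly before, the same section asks for each AE's potential relatedness to be recorded.

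Relatedness is then used in these places:

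- **Protocol 9.2.1, SAEs after consent and before dosing:** these follow the SAE reporting requirements and timelines "if it is considered reasonably possibly related to study procedure".
- **Protocol 9.2.1, SAEs learned of after discharge:** the sponsor must be told promptly if "he or she considers the event reasonably possibly related to the study treatment or study participation".
- **Protocol 9.2.1.1:** SUSARs are unlisted serious events "that the investigator identifies as related to study treatment or procedure".
- **Protocol 10.3.4 and SAP 6.11:** TEAEs are summarised by the investigator's answer; the SAP's wording is "by investigator classification of related to study treatment".

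The SAP takes the answer as given and does not redefine the term.

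**The concern.** The definition sets a higher bar than the term it defines. An investigator who believes that a drug, capsule or procedure could have caused an event, but cannot conclude that it did, should answer yes to the question and no under the definition. The scale has no middle category to absorb the difference.

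Two things are at stake. The first is classification. Possibly related serious events could fail the SUSAR definition, and possibly related TEAEs could be missing from the related-event summaries. The second is consistency. With two thresholds in one section, some investigators will use one and some the other, and the related-TEAE summaries would then mix two standards that cannot be separated afterwards.

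**Working it through.** No arithmetic applies, and the plan gives no figure to reproduce. The check compares the wording of the rule and then traces each use of the answer.

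**Step 1: the threshold.** Three elements of Section 9.2 can be set side by side.

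- Recording instruction: potential relatedness, a lower bar.
- Question: "has a reasonable possibility of being related to study treatment, study device, or a study procedure", also a lower bar.
- Definition of the term in that question: a causal relationship exists. It contains no may, could or suspected.

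The first two agree with each other and the third contradicts both. All three are current text in the body of the protocol.

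**Step 2: a test case.** Take an SAE that the investigator thinks may have been caused by treatment, without concluding that it was. The question gives yes and the definition gives no.

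**Step 3: where a no has an effect.**

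| Use | Depends on the answer? | Effect of a no |
|---|---|---|
| SUSAR definition (Protocol 9.2.1.1) | Yes, directly | Event not identified as related |
| Related-TEAE summaries (Protocol 10.3.4, SAP 6.11) | Yes, directly | Event not counted as related |
| Pre-dose SAE reporting (Protocol 9.2.1) | By inference | SAE timelines may not apply; event still in the eCRF |
| Post-discharge SAE notification (Protocol 9.2.1) | By inference | Sponsor may not be told |
| eCRF recording of every AE after consent (Protocol 9.2.1) | No | None |
| 24-hour alert for SAEs on study after dosing (Protocol 9.2.1) | No | None |
| All-SAE table (SAP 6.11.4) and all-TEAE tables (SAP 6.11) | No | None |
| CTT and other transit times, GSRS, BSFS, SBM (SAP 6.10) | No | None |
| Treatment-emergent constipation (SAP 6.10.4) | No; a constipation TEAE and/or a GSRS constipation score of at least 4 | None |

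The two rows marked as inference use the phrase reasonably possibly related, which is close to the defined term but not identical to it. Neither rule cites the definition. The pre-dose rule points back to Section 9.2, but for reporting requirements and timelines. No other definition is offered, so carrying the Section 9.2 meaning across is natural but not stated.

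**Step 4: size.** The documents give no AE or SAE rates and no expected split between possible and established causation. The effect runs from none, if every investigator applies the ordinary meaning of reasonable possibility, to every event judged possible but not established, if every investigator applies the definition literally.

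**The case against.** The best defence is that the sentence only explains what related means, namely causal rather than coincidental in time, and leaves reasonable possibility as the threshold. The request for potential relatedness supports that as the intention, and the literal reading empties the word possibility of meaning. But the sentence has reasonable possibility as its subject and says what that term means; it does not define related. The defence makes it likely that many investigators will use the lower bar in practice. It does not make the text say so.

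A second defence is that Protocol 9.2.1.1 refers to sponsor procedures for identifying and reporting SUSARs, and that post-dose SAEs on study are already with the sponsor within 24 hours. This reduces the practical risk. The documents do not say, however, that those procedures override an investigator's no.

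A reader might infer three stronger conclusions, none of which the documents support:

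- **SAEs in general would go unreported.** The 24-hour alert covers any SAE on study after dosing, whatever its cause, and all SAEs are tabulated.
- **Pre-dose SAEs, including those after the first capsule, would reach the sponsor only on a yes.** Every AE after consent is recorded in the eCRF without a causality condition. Protocol Appendix 2.2.1 describes the data capture system as provided by the sponsor, and Appendix 2.2 has the sponsor or its representatives review CRF data. At most, the speed of reporting is at risk. Post-discharge SAEs have no equivalent backstop in the text, and sites need not actively seek them.
- **The evidence on constipation would be distorted.** CTT is read by experts blind to treatment, the symptom measures come from patients, and neither the treatment-emergent constipation definition nor the all-TEAE tables use relatedness.

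**Conclusion.** The text is wrong as written, with low severity. The definition in Protocol 9.2 contradicts the question it serves and the potential-relatedness wording beside it. Followed literally, it misclassifies possibly related events for the SUSAR definition and for the related-TEAE summaries; those two effects follow directly from the text. Slower reporting of pre-dose SAEs and missed notification of post-discharge SAEs are plausible, on the assumption that the definition also governs the variant phrase in Section 9.2.1.

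The number of events affected cannot be computed. It depends on how many investigators follow the definition rather than the ordinary sense of the term, and on how many events fall between possible and established. No efficacy conclusion is affected.

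**What to change.** In the defining sentence of Protocol 9.2, replace the statement that a cause-and-effect relationship exists with one that such a relationship may exist, leaving the rest of the sentence as it is. Use the defined term, in the same form, in the two conditional reporting rules of Section 9.2.1 and in the SUSAR definition of Section 9.2.1.1, so that one threshold governs all of them. A definition requiring evidence that suggests causation would be a different bar: it could exclude events thought possible without positive evidence, so it matches the question less well.

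Leave the yes/no answer and the reporting timelines unchanged. The SAP needs no edit, because it uses the investigator's answer as recorded.

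The cost is a short wording change in the next amendment and a line in site training. The downside is that slightly more events will be recorded as related.

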9.2.1. Serious Adverse Events

An SAE is any AE from this study that results in 1 of the following outcomes:

- death
- initial or prolonged inpatient hospitalization
- a life-threatening experience (i.e., immediate risk of dying)
- persistent or significant disability/incapacity
- congenital anomaly/birth defect

- important medical events that may not be immediately life-threatening or result in death or hospitalization but may jeopardize the patient or may require intervention to prevent one of the other outcomes listed in the definition. Examples of such medical events include allergic bronchospasm requiring intensive treatment in an emergency room or at home, blood dyscrasias or convulsions that do not result in inpatient hospitalization, or the development of drug dependency or drug abuse.
- when a condition related to the AI pen necessitates medical or surgical intervention to preclude either permanent impairment of a body function or permanent damage to a body structure, the serious outcome of “required intervention” will be assigned.

All AEs occurring after signing the ICF are recorded in the eCRF and assessed for serious criteria. The SAE reporting to the sponsor begins after the patient has signed the ICF and has received study treatment. However, if an SAE occurs after signing the ICF, but prior to receiving study treatment, the SAE should be reported to the sponsor as per SAE reporting requirements and timelines (see Section 9.2) if it is considered reasonably possibly related to study procedure.

Study site personnel must alert Lilly or its designee of any SAE within 24 hours of investigator awareness of the event via a sponsor-approved method. If alerts are issued via telephone, they are to be immediately followed by official notification on study-specific SAE forms. This 24-hour notification requirement refers to the initial SAE information and all follow-up SAE information.

Pregnancy (during maternal or paternal exposure to study treatment) does not meet the definition of an AE. However, to fulfill regulatory requirements any pregnancy should be reported following the SAE process to collect data on the outcome for both mother and fetus.

Investigators are not obligated to actively seek AEs or SAEs in subjects once they have discontinued and/or completed the study (the patient disposition eCRF has been completed). However, if the investigator learns of any SAE, including a death, at any time after a subject has been discharged from the study, and he or she considers the event reasonably possibly related to the study treatment or study participation, the investigator must promptly notify Lilly.

